16.2 Appendix 2: Specific Renal Alert Criteria and Actions and Event Follow-up

Table 16-4 Specific Renal Alert Criteria and Actions

Renal Event	Actions
Confirmed serum creatinine increase 25 – 49%	
Consider causes and possible interventionsFollow up within 2-5 days
Serum creatinine increase 50% ⁺	
Consider causes and possible interventionsRepeat assessment within 24-48h if possibleConsider drug interruption or discontinuation unless other causes are diagnosed and correctedConsider participant hospitalization and specialized treatment
New onset dipstick proteinuria $\geq 3+$ OR Protein-creatinine ratio (PCR) $\geq 1\text{g/g Cr}$ (or mg/mmol equivalent as converted by the measuring laboratory)	
Consider causes and possible interventionsAssess serum albumin & serum total proteinRepeat assessment to confirmConsider drug interruption or discontinuation unless other causes are diagnosed and corrected
New onset hematuria $\geq 3+$ on urine dipstick	Assess & document 
Repeat assessment to confirmDistinguish hemoglobinuria from hematuriaUrine sediment microscopyAssess sCrExclude infection, trauma, bleeding from the distal urinary tract/bladder, menstruationConsider bleeding disorder
New evidence of clinically significant crystals on microscopy	Assess & document 
Repeat assessment to confirmAssess serum creatine, urea and electrolytesConsider causes and possible interventionsConsider drug interruption or discontinuation unless other causes are diagnosed and corrected

+ Corresponds to KDIGO criteria for Acute Kidney Injury

Additional specialized assessments are available to assess renal function or renal pathology.

(Note: In exceptional cases, when a nephrologist considers a renal biopsy, it is recommended to make slide specimen available for evaluation by the RSG to potentially identify project-wide patterns of nephrotoxicity.)

Whenever a renal event is identified, a detailed patient history and examination are indicated to identify and potentially eliminate risk factors that may have initiated or contributed to the event:

- Blood pressure assessment (after 5-minute rest, with an appropriate cuff size)
- Signs and symptoms like fever, headache, shortness of breath, back or abdominal pain, dysuria or hematuria, dependent or periorbital edema
- Changes in blood pressure, body weight, fluid intake, voiding pattern, or urine output
- Concomitant events or procedures such as trauma, surgical procedures, cardiac or hepatic failure, contrast media or other known nephrotoxin administration, or other diseases or causes, e.g. dehydration due to delirium, tumor lysis

Table 16-5 Renal Event Follow up

Assess, document and record in eCRF

- Urine dipstick and sediment microscopy evidence of DIN: crystals, red blood cells (dysmorphic/glomerular vs. non-dysmorphic/non-glomerular), white blood cells, tubular epithelial cells
- Blood pressure and body weight
- Serum creatinine, BUN, electrolytes (sodium, potassium, phosphate, calcium), bicarbonate and uric acid
- Urine output

Review and record possible contributing factors to the renal event (co-medications, other co-morbid conditions) and additional diagnostic procedures (MRI etc.) in the eCRF.

Monitor patient regularly (frequency at investigator's discretion) until -

- Event resolution: (sCr within 10% of baseline or PCR <1 g/g Cr, or ACR <300 mg/g Cr) or
- Event stabilization: sCr level with $\pm 10\%$ variability over last 6 months or protein:creatinine ratio stabilization at a new level with $\pm 50\%$ variability over last 6 months.
- Analysis of urine markers in samples collected over the course of the DIN event

16.3 Appendix 3: Cold challenge description and follow up procedures

- Room:
 - Ambient temperature of 4°C should be maintained. The temperature in the cold room should be monitored with a validated temperature monitoring device during the cold challenge. The temperature at the start and stop of the cold challenge should be documented in the eCRF. Any deviations outside 4-6°C should be documented in the source documents
 - Forced cooled air to simulate the condition to trigger acute FCAS.
 - Prior to the cold challenge patient should remain at room temperature ideally greater than 23°C
- Total duration:
 - 45 minutes from start to finish
- Patient monitoring:
 - During the cold challenge the clinical site staff must continuously monitor the participant to ensure the patient remains alert, oriented to time, place and person and is able to mobilize
 - Vital signs should be collected at baseline and then at least every 10 minutes and at completion of the cold challenge (captured in source documentation only)
 - Cold challenges should take place at sites with immediate access to equipment and trained staff for treating participants with FCAS in the case of an adverse event.
- The cold challenge must be stopped if any of the following criteria are met:
 - The participant requests to discontinue the cold challenge
 - The participant's body temperature is 35.0°C or below on two consecutive temperature readings
 - The criteria for an overall study stopping rule are met (see [Section 9.1.4](#))
- Participant instructions:
 - Participants should be wearing light clothing (e.g. t-shirt and shorts)
 - Participants can stand, sit or walk-around
 - Strenuous exercise is not allowed
- Passive rewarming post cold challenge:
 - Participants will be returned to an ambient temperature of approximately 23°C for at least 24 hours at the clinical site for clinical monitoring and to complete trial related procedures, this period may be extended as per medical judgement
 - The participant should be covered with blankets and other types of insulation, until normal temperature is restored, or fever develops as part of the FCAS episode

In addition, guidance and requirements provided by the local regulatory authorities or local site-specific standard operating procedures must also be followed, as applicable.

16.4 Appendix 4: Physician Global Assessment of Autoinflammatory Disease Activity

Figure 16-1 Physician Global Assessment of Autoinflammatory Disease Activity

Physician global assessment of autoinflammatory disease activity:

Absent Minimal Mild Moderate Severe *(tick only one)*

16.5 Appendix 5: Physician's Severity Assessment of Autoinflammatory Disease Signs and Symptoms

Figure 16-2 Physician's Severity Assessment of Autoinflammatory Disease Signs and Symptoms

1. Assessment of skin disease (urticarial skin rash):

Absent Minimal Mild Moderate Severe *(tick only one)*

2. Assessment of arthralgia:

Absent Minimal Mild Moderate Severe *(tick only one)*

3. Assessment of myalgia:

Absent Minimal Mild Moderate Severe *(tick only one)*

4. Assessment of headache/migraine:

Absent Minimal Mild Moderate Severe *(tick only one)*

5. Assessment of conjunctivitis:

Absent Minimal Mild Moderate Severe *(tick only one)*

6. Assessment of fatigue/malaise:

Absent Minimal Mild Moderate Severe *(tick only one)*

7. Assessment of other symptoms related to autoinflammatory syndrome:

Describe and assess symptoms:

Absent Minimal Mild Moderate Severe *(tick only one)*

8. Assessment of symptoms not related to autoinflammatory syndrome:

Describe and assess symptoms:

Absent Minimal Mild Moderate Severe *(tick only one)*

16.6 Appendix 6: Patients Global Assessment of Disease Activity

Figure 16-3 Patients Global Assessment of Disease Activity

CDFV890A12201	

Site No.	Subject No.	

Date of Assessment	

day	month	year	

	Site No.	Subject No.	Date of Assessment		day	month	year	Visit Name
Site No.	Subject No.								
Date of Assessment									
day	month	year							
Time of Assessment: ___/___/___									
Patients Global Assessment of Disease Activity									

Please rate your overall symptoms at this given time point (tick one only):									

 Absent Minimal Mild Moderate Severe

1.1 Scope of document

The Reporting and Analysis Plan (RAP) documents contain detailed information to aid the production of Statistics & Programming input into the Clinical Study Report (CSR) for trial “**CDFV890A12201**”.

The Statistical Analysis Plan (SAP) describes the implementation of the statistical analysis planned in the protocol.

1.2 Study reference documentation

Final study protocol amendment (v04) is available at the time of finalization of SAP.

1.3 Study objectives

1.3.1. Primary objective

Primary objective	Endpoint for primary objective

To assess the efficacy of DFV890 to reduce cold-induced inflammation in participants with FCAS	
Ratio of fold change from pre-challenge to the highest post-challenge value of white cell count (WCC) between treatment and screening period

1.3.2. Secondary objective

Secondary objective	Endpoint for secondary objective

To assess safety and tolerability of DFV890	
Safety endpoints (including vital signs, ECG parameters, safety laboratory assessment and adverse events)

To assess the efficacy of DFV890 to improve the signs and symptoms of FCAS	
Change from pre-challenge to post-challenge between treatment and screening period in:
Physician global assessment of autoinflammatory disease activityPhysician’s severity assessment of autoinflammatory disease signs and symptoms

To assess the effect of DFV890 on patient reported outcomes	
Change from pre-challenge to post-challenge between treatment and screening period in:

	
• Patients global assessment of disease activity
--	--

[figure not shown]
Commercially Confidential Information

1.4 Study design and treatment

This is an open-label, single-arm, multiple dose, phase II study to assess safety, tolerability and efficacy of DFV890 in participants with FCAS who show evidence of inflammatory activity after the cold challenge performed during screening. Approximately 6 participants with FCAS and confirmed NLRP3 gain-of-function mutations will be enrolled in the study.

Figure 1-1 summarizes the study design and shows the steps that will be followed in the study. The study consists of three periods: screening, treatment and follow-up.

Figure 1-1 Study Design Schematic

* Up to 12 months for participants with a historical screening cold challenge prior to protocol amendment 04.

Screening period: A period of up to 6 months (and up to 12 months for participants with a historical screening cold challenge prior to protocol amendment 04), when the participant's eligibility will be assessed at a screening visit and a cold challenge will be performed. During the screening cold challenge, participants will be domiciled for three days following a minimum of one week of recovery from the cold challenge prior to enrollment and initiation of treatment. The screening cold challenge can be conducted any time during the screening period, provided that Day 1 is conducted within 6 months (and within 12 months for participants with a historical screening cold challenge prior to protocol amendment 04; see below) of the Screening visit and all inclusion and none of the exclusion criteria are met. Historical screening cold challenge conducted in this study under the previous protocol version is acceptable, provided that Day 1 is conducted within 12 months of the Screening visit, and all inclusion and none of the exclusion criteria based on this amendment are met.

Treatment period: Eligible participants (defined as those participants who respond to the cold challenge) will then enter the treatment period where they will be administered oral DFV890 100 mg b.i.d. for 3 days, one last dose will be administered in the morning of Day 4 followed by a cold challenge. Participants will be admitted to the clinic in the morning of Day 3 (the day prior to cold challenge) and will be domiciled for a total of three days or longer (if needed). On the morning of Day 4, pre-challenge assessments will be performed, and then cold challenge

will last for 45 minutes. After the end of the cold challenge, participants will be monitored until the next morning (Day 5) and discharged after the last assessment on Day 5 or later.

Follow up period: Participants will be then followed-up for an end of study evaluation at the study competition visit, approximately 10 days after last dose and a post study safety contact will occur 30 days after last dose. The total study duration from screening until study completion is expected to be up to 7 months (and up to 13 months for participants with a historical screening cold challenge prior to protocol amendment 04).

Unscheduled visits: Participants will be instructed to contact the investigator if they develop rash or pruritus between visits from Day 1 to the Study completion visit. An unscheduled visit should be considered based on clinical findings and severity of rash or pruritus and related assessments performed. Unscheduled visits may be performed at an alternative Sponsor-approved site (e.g. satellite site that may be more convenient to the participant) if agreed by the PI who will maintain the investigator responsibilities, and only as permitted by local regulations.

2 First interpretable results (FIR)

Commercially Confidential Information

3 Interim analyses

No interim analysis is planned for this trial.

Interim analyses may be conducted to support decision making concerning the current clinical study, the sponsor's clinical development projects in general or in case of any safety concerns.

4 Statistical methods: Analysis sets

The safety analysis set will include all participants that received any study drug.

Commercially Confidential Information

The PD analysis set will include all participants with no protocol deviations with relevant impact on PD data.

The analysis sets and protocol deviation codes are related as follows:

Table 4-1 Protocol deviation codes and analysis sets

Category	Text description of deviation	Data exclusion
Deviation code		
Participants are excluded from safety analysis in case of these PDs:		Exclude participant from safety analysis set
INCL01	Informed consent form not obtained	Yes

Commercially Confidential Information

Participants are excluded from PD analysis in case of these PDs:		Exclude participant from PD analysis set
INCL01	Informed consent form not obtained	Yes
INCL08	relative WCC increase <40% compared to pre-challenge after cold challenge at screening period	Yes

If updates to this table are needed, an amendment to the SAP needs to be implemented prior to DBL.

The number and percentage of participants in each analysis set will be summarized. Participants excluded from any analysis set(s) along with the reason(s) for their exclusion will be listed.

All protocol deviations will be listed by participant and the number and percentage of participants with protocol deviations will be summarized.

Commercially Confidential Information

Commercially Confidential Information

6 Statistical methods for Pharmacodynamic (PD) parameters

All participants within the PD analysis set will be included in the PD data analysis.

6.1 Primary objective

The primary efficacy objective of this study is to assess the efficacy of DFV890 to reduce cold-induced inflammation in participants with FCAS.

6.1.1 Variables

Fold change from pre-challenge to the highest post-challenge value of total WCC is the primary efficacy variable. The highest post-challenge value is based only on post-challenge measurements within the cold challenge visit (up to and including 8 hours post-challenge). Lower induction of total WCC is considered a favorable outcome.

Fold change from pre-challenge to a post-challenge value of WCC is defined as the ratio of the post-challenge WCC value to the pre-challenge WCC value, i.e.:

$$\text{Fold change} = \frac{\text{post challenge WCC}}{\text{pre challenge WCC}}$$

6.1.2 Descriptive analyses

A geometric mean (SE) plot of fold change from pre-challenge to post-challenge over time will be provided by period.

6.1.3 Statistical model, assumptions and hypotheses

Commercially Confidential Information

The primary objective will be achieved and DFV890 will be considered efficacious in treating cold-induced inflammation in participants with FCAS if the estimated ratio of fold changes from pre-challenge to highest post-challenge WCC between treatment and screening period is:

- (1) Statistically significant (p-value<0.10), and
- (2) Less than 80%.

Note: The highest post-challenge WCC value per period will be considered in the primary model analysis. This implies that the highest post-challenge WCC value will not necessarily occur at the same post-challenge time point in both periods.

6.1.3.1 Handling of remaining intercurrent events of primary estimand

Interruption of study treatment for any reason will be ignored.

6.1.3.2 Handling of missing values not related to intercurrent event

Due to the limited sample size, all available data will be included in the model. This corresponds to assuming a missing at random strategy.

Commercially Confidential Information

Commercially Confidential Information

Commercially Confidential Information

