2.1 Primary estimand

The primary clinical question of interest is: does DFV890 prevent flares triggered by the cold challenge as indicated by proportional reduction in the fold change from pre-challenge to the highest post-challenge value of WCC between treatment and screening periods in participants with FCAS?

It has been shown ([Hoffman et al 2004](#)) that the fold change in WCC from pre-challenge to post-challenge can capture the treatment effect in the acute flare situation triggered by the cold challenge. Hence the choice of the primary estimand is considered as the ratio of fold change from pre-challenge to highest post-challenge WCC values between treatment and screening.

The primary estimand is described by the following attributes:

[figure not shown]
1. Population: participants with a genetic diagnosis of FCAS in association with a clinical history and investigations consistent with FCAS, who show evidence of inflammatory activity after the cold challenge performed during screening. Further details about the population are provided in [Section 5](#).
2. Endpoint: fold change from pre-challenge to the highest post-challenge value of WCC. This is measured as the ratio of highest post-challenge and the pre-challenge value of WCC. The highest post-challenge value is based only on post-challenge measurements within the cold challenge visit (up to and including 8 hours post-challenge; i.e. 9 hours post-dose).
3. Treatment of interest: DFV890
4. Summary measure: ratio of treatment fold change and screening fold challenge of WCC value.

3 Study design

This is an open-label, single-arm, multiple dose, phase II study to assess safety, tolerability and efficacy of DFV890 in participants with FCAS who show evidence of inflammatory activity after the cold challenge performed during screening. Approximately 6 participants with FCAS and confirmed NLRP3 gain-of-function mutations will be enrolled in the CDFV890A12201 study.

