4.6.2 Potential risks to study participants

The risk to participants with FCAS in this trial may be minimized by compliance with the eligibility criteria and study procedures, as well as close clinical monitoring, follow-up, minimal duration of the study treatment and pre-specified study stopping rules.

The cold challenge procedure was developed to study the acute inflammatory mechanisms after general cold exposure in FCAS patients and to investigate the effect of pretreatment with IL-1 blocking therapeutics to enable the clinical development of such therapeutics. Participants with a clinical history of transient self-limiting rash, fever and/or arthralgia that are pathognomonic of FCAS following cold exposure that resolve with warmth will undergo two controlled cold challenges while domiciled at the clinical site under medical supervision to trigger a transient and monitorable inflammatory response. Following the 45-minute cold challenge, participants will be returned to an ambient temperature of approximately 23°C for at least 24 hours at the clinical site, to ensure resolution of the inflammatory response.

The design of the cold challenge procedure is based on the clinical characteristics of the acute episodes in FCAS patients where a mean duration of generalized cold exposure of 52 minutes (range 5-180 minutes) was reported to trigger a self-limiting episode with onset of symptoms 150 minutes (range 10-480 minutes) after generalized cold exposure, with the absolute change in temperature (ambient to low) being an important factor in precipitating episodes (Hoffman et al 2001, Johnstone et al 2003). Importantly, environmental generalized cold exposure (e.g. cold damp weather) would similarly cause an inflammatory episode in many untreated FCAS patients experiencing baseline daily symptoms, often with diurnal pattern of episodes in the afternoon or evening that resolve by morning following rewarming in bed overnight. The cold challenge as described in the present protocol models the real life situation of exposure to mildly cold weather conditions and is expected to trigger typical signs and symptoms of an acute episode in FCAS patients including a low-grade fever, rash and arthralgia beginning approximately 1 hour after challenge, peaking at 4-8 hours and abating with warming by the next day with no reports of acute complications during the challenge or long-term sequelae in patients (Hoffman et al 2004, Ross et al 2008).

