5.1 Inclusion criteria

Participants eligible for inclusion in this study must meet **all** of the following criteria:

1. Written informed consent must be obtained before any study-specific assessment is performed.
2. Participants must be able to communicate well with the investigator and to understand and comply with the requirements of the study.
3. Male and female participants aged between 18 - 80 years (for France 18 - 60 years) inclusive at the time of screening will be included.
4. Participants must have a body mass index (BMI) within the range of 18 - 35 kg/m² (BMI = Body weight (kg) / [Height (m)]²) at Screening, Screening Cold Challenge Admission visit and Day 1 pre-dose.
5. Participant with a genetic diagnosis of FCAS (this analysis may be performed as part of screening if not readily available).
6. Clinical history and investigations consistent with FCAS, in the absence of a history or diagnosis of amyloidosis and/or organ damage (e.g. deafness, periorbital edema, lymphadenopathy, and serositis).
7. Evidence of inflammatory disease activity during the screening period before the admission to the screening cold challenge, captured by the Physician global assessment of autoinflammatory disease activity > minimal, recorded at Screening Cold Challenge Admission visit.
8. Participants who have evidence of inflammatory activity after the screening cold challenge, as assessed by a relative increase in WCC of at least 40% compared to pre-challenge.

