^x Assessment to be recorded in the clinical database or received electronically from a vendor

^s Assessment to be recorded in the source documentation only

¹ Visit Numbers given for internal programming purpose only

² Assessments to be conducted prior to first dose

³ Assessments to be conducted prior to the morning dose

⁴ Admission can be delayed with a maximum of one day and treatment hence prolonged to with one day. This option should only be used under exceptional circumstances

⁵ To confirm eligibility, available historical CYP2C9 genotyping results confirming the absence of the CYP2C9*3/*3 variant previously issued in frame of this study are acceptable for re-screened participants

⁶ Participant domiciliation may be prolonged at the discretion of the investigator and patient

⁷ The start of the cold challenge is at 1 h and the duration is 45 minutes. The screening cold challenge should be initiated 1 h after meal and treatment cold challenge 1 h after treatment administration.

⁸ Where possible, white cell count should be included as part of hematology sampling, rather than collecting a separate sample

⁹ Commercially Confidential Information

¹⁰ To be collected at 0 h prior to morning dose and 12 h after previous evening dose the day before

¹¹ To be collected at 1 h postdose, prior to initiation of cold challenge

¹² Commercially Confidential Information

¹³

¹⁴ Also applicable in case of early discontinuation

¹⁵ 30 days after last dose

¹⁶ Vital signs to be collected every 10 minutes during the cold challenge and at the end of the cold challenge

¹⁷ The Physician Global Assessment of Autoinflammatory Disease Activity conducted at the Screening Cold Challenge Admission visit must capture evidence of disease flare (> minimal) occurring during the screening period

¹⁸ The screening cold challenge can be conducted any time during the screening period (the visits "Admission", "Screening Cold Challenge" and "Discharge" must occur on 3 consecutive days), provided that Day 1 is conducted within 6 months (and within 12 months for participants with a historical screening cold challenge prior to protocol amendment 04) of the Screening visit

¹⁹ Participants can be admitted to the Screening Cold Challenge visit only when all eligibility criteria are confirmed, except inclusion criterion 8 which is assessed during the screening cold challenge

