7.3 Graphical presentation

Scatterplots with overlaid median will be created to visualize trends in longitudinal safety data (vitals, ECG, lab parameter).

Commercially Confidential Information

Commercially Confidential Information

10 Consideration due to COVID-19

Due to the COVID-19 pandemic, it may not be possible to perform some procedures as per protocol. All deviations due to COVID-19 will be listed separately to other deviations and may also be tabulated.

Observations that were impacted due to COVID-19, may be excluded from the primary analyses, for example including (but not limited to) observations taken at participant's house instead of site, and separately explored to identify if there is an impact of them on the analyses.

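### Should WCC time points be matched between periods when a post-challenge sample is lost in only one of them?

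*SAP*

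**What the plan says.** SAP 6.1.1 and Protocol 2.1 define the fold change as the post-challenge WCC divided by the pre-challenge WCC of the same period. On the window, the SAP states: "The highest post-challenge value is based only on post-challenge measurements within the cold challenge visit (up to and including 8 hours post-challenge". Protocol 2.1 fixes the same limit on the dosing clock ("up to and including 8 hours post-challenge; i.e. 9 hours post-dose"), and footnote 7 to Protocol Table 8-1 adds: "The start of the cold challenge is at 1 h and the duration is 45 minutes". The table columns after the challenge and inside the window are therefore 2, 3, 5 and 9 h, that is 1, 2, 4 and 8 h after the challenge starts.

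SAP 6.1.3 takes one maximum per period and accepts that the two peaks may differ in time: "This implies that the highest post-challenge WCC value will not necessarily occur at the same post-challenge time point in both periods".

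For missing values, SAP 6.1.3.2 and Protocol 12.4.4 share a sentence, "Due to the limited sample size, all available data will be included in the model", and label it missing at random. Redacted blocks follow both paragraphs, and the statistical model itself is redacted. The WCC row for the challenge visits is not visible in Table 8-1.

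SAP section 10 adds a discretionary route: "Observations that were impacted due to COVID-19, may be excluded from the primary analyses". Its example is sampling at home.

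**The concern.** A maximum over fewer samples can only stay the same or fall. If one period loses its peak sample, the participant's value is not missing; it is present and understated. A missing-at-random assumption does not repair that, because the model sees a complete pair.

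The last sample looks most exposed. If WCC is drawn at the table columns, losing the 9 h sample leaves nothing after 4 h post-challenge. Protocol 4.6.2 describes signs and symptoms (not WCC) as "beginning approximately 1 hour after challenge, peaking at 4-8 hours and abating with warming by the next day".

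With about six pairs, and success requiring both p<0.10 and an estimated ratio below 80%, a lost treatment peak would favour DFV890 without leaving a trace in the test. A lost screening peak would work against it, or could take a participant below the entry threshold ("as assessed by a relative increase in WCC of at least 40% compared to pre-challenge").

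**Working it through.** **1. The plan's own figure.** Inputs from Protocol 12.8.1: ratio 0.50, log-scale SD 0.5, n = 6; criterion from 12.4.2. With a paired t test on the log ratio, SE = 0.5/√6 = 0.204 and ln 2/0.204 = 3.40 on 5 df. The joint success probability is 96.3% one-sided and 89.4% two-sided, against a stated figure of at least 90%. This fits reading 0.5 as the SD of the paired log ratio. The sidedness of the test is not visible, so both are shown where available.

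**2. Direction.** R = (max T / pre T) / (max S / pre S). Illustrative values: pre-challenge 7 in both periods; screening 8, 10, 13, 14; treatment 7.5, 8.5, 9.8, 11.2.

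- Complete: (11.2/7)/(14/7) = 1.60/2.00 = 0.80
- Treatment peak lost: (9.8/7)/2.00 = 1.40/2.00 = 0.70
- Screening peak lost: 1.60/(13/7) = 1.60/1.857 = 0.86
- A non-peak treatment sample lost: 0.80, unchanged

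This requires that the pre-challenge value and another post-challenge value remain. Without the pre-challenge value the fold change is undefined.

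**3. Weight among six.** The geometric mean ratio is multiplied by (0.70/0.80)^(1/6) = 0.875^(1/6) = 0.978 for the treatment loss, and by (0.8615/0.80)^(1/6) = 1.012 for the screening loss.

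**4. False success when there is no effect.** Assumptions: n = 6; paired log SD 0.5; samples at 1, 2, 4 and 8 h; sample noise SD 0.05 or 0.15 on the log scale; one participant loses the 8 h sample. Assumed fold-change courses at peak 2.0 are late (1.1, 1.3, 1.8, 2.0), plateau (1.3, 1.6, 1.9, 2.0), mid (1.2, 1.6, 2.0, 1.7) and early (1.6, 2.0, 1.7, 1.4). The documents give no WCC course and no loss rate.

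Late, plateau and mid courses, ignoring selection by the 40% rule:

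| | One-sided | Two-sided |
|---|---|---|
| No loss | 8.4–8.5% | 4.5–4.6% |
| Treatment sample lost | 8.4–10.1% | 4.5–5.5% |
| Screening sample lost | 6.7–8.4% | 3.6–4.5% |

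An early course changes these by at most 0.1 point.

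With selection by the 40% rule (person-effect SD 0.3), a lost treatment sample adds 0 to 3.0 points one-sided. A lost screening sample takes off 0 to about 2 points when eligibility is judged on the maximum actually observed. The figure of 3.2 points arises only if eligibility is judged on a complete maximum that nobody saw. For scale, the one-sided no-loss rate runs from about 10% at an assumed peak of 3.0 to 25.0% at 1.7, far more than any effect of one lost sample.

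**5. Does matching time points help?** If both periods share one time course and eligibility is ignored, it restores the no-loss rate. Neither condition can be relied on.

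- *Different courses.* Screening 1.1, 1.6, 2.0, 1.9; treatment 1.0, 1.1, 1.3, 1.8; the screening 8 h sample is lost. The true ratio is 1.8/2.0 = 0.90. The plan's rule also gives 0.90. Matching discards the observed treatment peak and gives 1.3/2.0 = 0.65, an error in favour of DFV890 where there was none.
- *Eligibility on the observed maximum.* With a lost screening sample, late course and noise 0.15, matching raises one-sided false success above the no-loss rate: 22.7% to 23.7% at peak 1.7, and 16.9% to 17.8% at peak 2.0.
- *Attenuation.* Treatment flat at 1.0; screening 1.8 at 4 h and 2.0 at 8 h; the treatment 8 h sample is lost. Matching gives 1.0/1.8 = 0.56 instead of 0.50.
- *Dropping the pair* when no late time point is shared cuts success at a true ratio of 0.50 from 96.4% to 92.7% (two-sided 89.5% to 81.3%).

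**The case for a change.** The best case for a change is that the mechanism is certain from the definitions, the sample is tiny, the study is open-label, and a paragraph fixed before database lock costs almost nothing. If both the 4 h and 8 h samples were lost in one treatment period, one-sided false success could reach 13.7% (peak 2.0, no selection), against 8.6–8.7% with that pair set to missing.

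The mechanism stands. The rest is weaker. The visible text is not silent: highest value per period, all available data, is a deterministic rule that leaves the analyst no choice to make after seeing results. The discretionary COVID-19 clause is a minor route, because participants are domiciled for both challenges. The 13.7% figure needs two of four assumed samples lost in the same period. The low cost does not survive step 5: matching replaces the defined endpoint for the affected pair, discards valid observations and can push the ratio in either direction.

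Nor is the absence of a rule established. The redactions sit where one would be written, and the protocol's contents list shows a redacted entry between 12.4.4 and 12.5.

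**Conclusion.** No change to the plan. A peak sample lost in one period understates that period's fold change, but the effect is conditional and small: 0 to about +3 points of one-sided false success for a treatment loss, and 0 to about -2 for a screening loss. Those sizes rest on assumed WCC courses, assumed sampling times, a paired log SD of 0.5 and a single affected participant. Nothing in the documents suggests that samples will be lost.

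The choice is a fair trade-off. The highest available value per period keeps the stated endpoint and every observation, at the price of an occasional understated maximum. Matching exchanges that for an error that depends on whether the two periods peak together, which SAP 6.1.3 explicitly does not assume. If a sample is lost, the time-course plot in SAP 6.1.2 and the listing of protocol deviations in SAP section 4 give the analyst a natural place to note the affected participant and judge whether the peak was missed. With six participants that can be done case by case, leaving the primary analysis as written.
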